## 9 STATISTICAL CONSIDERATIONS

#### 9.1 SAMPLE SIZE

This is a phase 2 study designed to assess the overall response rate (CR + PR) and progressionfree survival (PFS) of Umbralisib in treatment naïve patients with CLL. The primary endpoint is the overall response rate (ORR) from the time of treatment. The study will plan to enroll up to 40 subjects, and assuming 10% attrition, the study will have approximately 35 subjects remaining for analysis. Any subjects who are screen failures are not considered enrolled and may be replaced to meet the accrual goal. Enrollment is expected to be completed in approximately 18 months with 24 months follow up. The ORR for the standard of care is about 60%. We expect that Umbralisib treatment could lead to 80% ORR. A Simon 2-stage minimax design that differentiates ORRs of 0.60 (null hypothesis) and 0.80 (alternative hypothesis) will be used to assess treatment efficacy, with the probabilities of a type I error (falsely accepting a non-promising therapy) and type II error (falsely rejecting a promising therapy) both set at 0.10. Twenty seven patients will be accrued in the first stage of the study. If 18 or fewer patients have a response, then the study will be terminated and declared negative. If 19 or more patients have a response, then an additional 8 patients will be accrued to the second stage. At the conclusion of the study, if 25 or more patients have a response out of a total of 35 patients enrolled, the regimen will be considered worthy of further investigation.

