#### 9.3 STUDY POPULATIONS

Two study populations, intent-to-treat (ITT) and safety populations, are pre-defined for this study. The ITT population will include all enrolled patients who provide some efficacy assessments and the safety population will include all patients who take at least one dose of study medication. The efficacy analyses will be based on ITT population and the safety analyses will be based on the safety population.

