#### 9.9 STATISTICAL ANALYSES

## 9.9.1 PRIMARY EFFICACY VARIABLE - PFS

The two primary efficacy outcomes are overall response rate (ORR) and progression-free survival (PFS). Time to progression event "Survival" curve will be presented using Kaplan-Meier method. Median time to event and the 95% confidence interval of the median times will be presented, if estimable. Median time to event will be tested against the null hypothesis value using a one-sample (one-sided) log-rank test.

PFS is defined as the interval from Cycle 1, Day 1 to the earlier of the first documentation of definitive disease progression or death from any cause.

Overall Response Rate (ORR) will be determined according to the criteria of the International Workshop on Chronic Lymphocytic Leukemia (Hallek et al. 2018).

We will estimate Overall Response Rate (ORR), which is defined as percent of patients who achieve CR or PR. We will also estimate exact 95% confidence intervals for the response rates. These will be followed by additional logistic regression analyses model to adjust for demographic and baseline parameters.

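### Must the exact 95% confidence interval for ORR in section 9.9.1 be adjusted for the two stages, or matched to the one-sided 0.10 go rule?

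*Combined protocol and SAP*

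**What the plan says.** Section 9.1 (Sample Size), repeated in the synopsis under Statistics, sets the decision procedure: "A Simon 2-stage minimax design that differentiates ORRs of 0.60 (null hypothesis) and 0.80 (alternative hypothesis"). It "will be used to assess treatment efficacy, with the probabilities of a type I error" and a "type II error (falsely rejecting a promising therapy) both set at 0.10". Type I error is described there as wrongly accepting a poor therapy, so it is one-sided. "Twenty seven patients will be accrued in the first stage of the study"; the trial stops if 18 or fewer respond. Otherwise 8 more are added, and the regimen succeeds "if 25 or more patients have a response out of a total of 35 patients enrolled".

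Section 9.9.1 turns to estimation. After defining ORR as the percentage with CR or PR, it adds: "We will also estimate exact 95% confidence intervals for the response rates". It does not say whether the exact method allows for the two stages, and it plans no other interval or bound for ORR. Section 9.2 sets a two-sided 0.05 level for tests, but only where nothing else is stated, so the Simon rule keeps its own level.

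**The concern.** Two things catch the eye.

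- **Stages.** The usual exact (Clopper-Pearson) interval assumes a fixed sample. Here some paths to a given total are impossible, because the trial stops at 18 or fewer of 27. An interval that ignores this could have the wrong coverage.
- **Level.** A two-sided 95% interval tests at 0.025 in its lower tail, while the go rule works at 0.10. A trial with 25 to 27 responders of 35 would be declared a success beside an interval that still contains the 60% null rate.

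If the interval were invalid, or if the plan let it compete with the rule, the primary conclusion would be open to dispute. The remedy that suggests itself is an exact interval built on the two-stage sample space, plus a one-sided 90% lower bound to match the rule.

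**Working it through.** **Inputs** (section 9.1): p0 = 0.60, p1 = 0.80, n1 = 27, stop at 18 or fewer, n2 = 8, go at 25 or more of 35. The interval level, 95%, is from section 9.9.1.

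**1. Reproduce the design.** With x the stage 1 count,

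P(go | p) = Σ over x = 19 to 27 of P(Bin(27, p) = x) × P(Bin(8, p) ≥ 25 − x).

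This gives 0.0965 at p = 0.60 and 0.9003 at p = 0.80. A search over designs returns the same one as minimax (18/27, 24/35). The stated rule and error rates are correct.

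**2. Compute the 95% limits both ways.** The single-stage limits are Clopper-Pearson with n = 35. The two-stage limits rank all stage 1 stops below all stage 2 totals and invert the exact tails: the lower limit solves P(total ≥ s, trial continued | p) = 0.025. One-sided p is taken at 0.60.

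| Responders of 35 | Rule | 95% lower limit, single-stage | 95% lower limit, two-stage | p, single-stage | p, two-stage |
|---|---|---|---|---|---|
| 24 | no go | 50.7% | 52.4% | 0.195 | 0.137 |
| 25 | go | 53.7% | 54.4% | 0.1123 | 0.0965 |
| 26 | go | 56.7% | 56.9% | 0.0575 | 0.0554 |
| 27 | go | 59.9% | 59.9% | 0.0260 | 0.0260 |
| 28 | go | 63.1% | 63.1% | 0.0102 | 0.0102 |

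The two methods must agree from 27 upward. Stage 2 adds at most 8 responders, so a total of 27 needs at least 27 − 8 = 19 in stage 1, and the early stop excludes no such path. At 25/35 the full intervals are 53.7% to 85.4% and 54.4% to 85.6%.

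On either method the 95% interval includes 60% up to 27/35 and excludes it from 28/35. The stage adjustment changes no conclusion against 60%. No result that fails the rule has an interval above 60%.

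**3. Check coverage under the real design.** For each true p, add the two-stage probabilities of all outcomes whose interval contains p (n = 27 if stopped, n = 35 otherwise). Over p = 0.01 to 0.99 in steps of 0.001, minimum coverage is 0.951 for the single-stage interval and 0.950 for the two-stage one. The ordinary interval has no deficit to repair.

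**4. Separate the level effect.** At ORR 0.80, the chance of 25, 26 or 27 of 35 is 0.053 + 0.102 + 0.146 = 0.301, or 0.301 / 0.900 = 33% of successes. These are the trials in which a go stands beside an interval containing 60%. Step 2 shows that the two-stage method leaves all three as they are.

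**5. Find where the stages could matter.** At the rule's own level (one-sided 90% lower bound), 25/35 gives 59.4% ignoring the stages and 60.2% allowing for them. Only there does the method change the answer. That outcome has probability 0.053 at ORR 0.80, or 0.053 / 0.900 = 5.9% of successes. The plan contains no bound at this level.

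**The case for a change.** The best case for the concern is about transparency. If the drug performs as hoped, about one success in three will be reported beside an interval that contains 60%, and the plan offers no sentence to explain it. A reader who then computes an ordinary one-sided 90% bound at 25/35 gets 59.4% and seems to refute the go decision, whereas a design-based bound of 60.2% agrees with it. Choosing a method after seeing such a result could look selective.

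It is true that the method is unnamed, and a sentence would help a reader. But the word exact does not exclude a two-stage method, and at the planned 95% level the choice shifts the lower limit by 0.7 percentage points at the cut-off (54.4 − 53.7). The conflict at 25/35 arises only if one adds a bound that the plan does not have and then computes it without the stages. The coexistence of a go with an interval containing 60% is ordinary: section 9.1 makes a screening decision at 0.10, and section 9.9.1 describes precision at 95%.

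A related question is what happens if the number analysed is not 35. Section 9.1 expects that "the study will have approximately 35 subjects remaining for analysis" and section 9.3 says "The ITT population will include all enrolled patients who provide some efficacy assessments". With 27 in stage 1 and 36 analysed, 25 responders would give a p-value of 0.121. That concerns the denominator of the decision rule. It is a separate matter and does not make the interval wrong.

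**Conclusion.** The concern does not hold. The Simon rule is correctly derived and is the only stated criterion for ORR; nothing in section 9.9.1 lets the interval override it. The planned exact 95% interval is valid under the two-stage design even if computed as single-stage (minimum coverage 0.951), and allowing for the stages changes no conclusion against 60%. The inclusion of 60% at 25 to 27 of 35 follows from the two levels and would remain under the two-stage method. No decision, sample size or error rate is affected. What is left is an unnamed method and an optional extra bound, which are matters of reporting preference.

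This rests on 27 + 8 = 35 patients analysed, on Clopper-Pearson as the single-stage exact method, and on the ordering of two-stage outcomes described above.

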## 10 SAFETY REPORTING AND ANALYSIS

#### 10.1 SAFETY ANALYSES

Safety evaluations will be based on the incidence, intensity, and type of adverse events, as well as on clinically significant changes in the patient's physical examination, vital signs, and clinical laboratory results. Safety analyses will be performed using the safety population. Safety variables will be tabulated and presented by the dose of umbralisib study drug actually received. Exposure to study treatment and reasons for discontinuation of study treatment will also be tabulated.

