# 4. STUDY DESIGN

#### 4.1 OVERVIEW OF STUDY DESIGN

This study is designed as a Phase 2, single-center, single-arm trial to evaluate the ORR and PFS of umbralisib in treatment naïve CLL patients requiring therapy. Daily doses of oral umbralisib will be administered in the absence of disease progression, unacceptable toxicity, or withdrawal from treatment. Treatment cycles are 4 weeks, with the efficacy evaluations within 14 days prior to Cycle 4, Day 1 for Cycle 3 assessment, and within 14 days prior to Cycle 13, Day 1 for Cycle 12 assessment, and at any other time point to confirm progression. Patients who fail to achieve a partial or complete response to umbralisib at the Cycle 3 assessment will discontinue study treatment. At that time, patients- will be provided appropriate options to receive established frontline therapy. Patients who demonstrate a partial or complete response will be treated until disease progression, unacceptable toxicity, or the end of the study. Enrollment will be up to 35 patients.

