#### 4.2 REGISTRATION/ENROLLMENT

Following Screening, qualified patients will receive the following:

• Umbralisib 800 mg once daily

During the study period, all patients will be evaluated for response by CT or MRI within 14 days prior to Cycle 4, Day 1 for Cycle 3 assessment, and within 14 days prior to Cycle 13, Day 1 for Cycle 12 assessment, and at any other time point to confirm progression. Patients who fail to achieve a partial or complete response to umbralisib at the Cycle 3 assessment will discontinue study treatment. At that time, patients- will be provided appropriate options to receive established frontline therapy. Patients who demonstrate a partial or complete response will be treated until disease progression, unacceptable toxicity, or the end of the study.

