#### 6.3 DOSING DELAYS AND MODIFICATIONS

Patients should be assessed clinically for toxicity at each visit using the NCI CTCAE v5.0 (http://evs.nci.nih.gov/ftp1/CTCAE/CTCAE) grading scale. Dose delay and/or modification guidance is for adverse events considered at least possibly related to the study drug. If cytopenias are deemed related to the underlying disease rather than study drug, dose modifications are not required, or are per investigator discretion.

Umbralisib should be discontinued if treatment is delayed for greater than 8 weeks due to toxicity unless the Principal Investigator approves restarting treatment. If the subject discontinues treatment but has not progressed, the subject should be followed for progression. If a patient withdraws consent or has documented progression, an end of study visit should be completed.

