#### TABLE 3: STUDY DRUG DOSE LEVELS

| Study Drug | Starting Dose | 1 st Dose Reduction | 2 nd Dose Reduction |
|------------|---------------|--------------------------------|--------------------------------|
| Umbralisib | 800 mg        | 600 mg                         | 400 mg                         |

A maximum of two dose level reductions are allowed for umbralisib. If a patient requires a dose reduction of umbralisib due to study drug related toxicity, the dose may not be reescalated. If further evaluation of the toxicity reveals the event was not related to umbralisib, this should be recorded in the medical record and dose re-escalation to the next higher dose level may be considered at the discretion of the investigator.

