## 10.4.1 ABNORMAL LABORATORY VALUES AND VITAL SIGNS

The reporting of abnormalities of vital signs as adverse events should be avoided. Abnormalities of vital signs should not be reported unless any criterion for an SAE is fulfilled, the vital signs abnormalities cause the patient to discontinue study treatment, or the investigator insists that the abnormality should be reported as an AE. Abnormal laboratory results should be recorded as an adverse event if they are associated with an overdose, require or prolong inpatient hospitalization, or are otherwise considered clinically significant by the investigator. If an abnormal laboratory value or vital sign is associated with clinical signs and/or symptoms, the sign or symptom should be recorded as an AE, and the associated laboratory value or vital sign should be considered additional information to record related to the AE. If the laboratory abnormality is a sign of a disease or syndrome, only the diagnosis needs to be recorded on the SAE Report Form or AE eCRF.

Clinical Laboratory Results will be summarized. Summary statistics for actual values and for changes from baseline will be tabulated for laboratory results by scheduled visit. Patients with laboratory values outside of the normal reference range at any post-baseline assessment will be summarized and graded per NCI CTCAE Version 5.0 when applicable. Patient incidence of abnormal laboratory results will be summarized by treatment group and maximum grade for each abnormal laboratory finding.

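### Section 10.1 splits the safety tables by dose actually received in a single-arm, single-starting-dose trial, so the columns are formed largely by toxicity, and no all-patients column is required

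*Combined protocol and SAP*

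**What the plan says.** Section 10.1 gives the only general column rule for safety: "Safety variables will be tabulated and presented by the dose of umbralisib study drug actually received". It does not say whether that means starting dose, dose at event onset, last, lowest, modal or average dose.

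The design gives no assigned dose groups. Section 4.1: "This study is designed as a Phase 2, single-center, single-arm trial to evaluate the ORR and PFS of umbralisib". Section 4.2 gives every qualified patient "Umbralisib 800 mg once daily". Table 3 lists 600 mg and 400 mg only as first and second reductions, and adds: "A maximum of two dose level reductions are allowed for umbralisib". Section 6.3 states the trigger: "Dose delay and/or modification guidance is for adverse events considered at least possibly related to the study drug". Below Table 3: "If a patient requires a dose reduction of umbralisib due to study drug related toxicity, the dose may not be reescalated". The sentence after that lets the investigator consider moving back up a level if the event turns out not to be related to umbralisib.

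Four other places bear on the tables. Section 9.3 puts everyone dosed at least once in the safety population. Section 9.6 counts patients with dose modifications, by cycle and overall. Section 10.3 plans tables of related events, deaths, SAEs and events causing treatment discontinuation, without naming columns. Section 10.4.1 says of laboratory results: "Patient incidence of abnormal laboratory results will be summarized by treatment group and maximum grade".

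**The concern.** A split by dose is informative when dose is assigned before the outcome is seen. Here the order is reversed: a patient is at 600 mg or 400 mg because something happened at a higher dose. Sorting patients by dose received therefore sorts them, in large part, by whether they had toxicity.

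Safety and tolerability are a secondary objective (Section 2.1). The figure a reader needs is the incidence of each event among all patients who started at 800 mg, whatever dose they later took. As written, the plan does not require that figure in the safety tables. It asks for a display that could be misread as a dose-toxicity relation and, under some placements, would understate the rate shown for 800 mg.

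**Working it through.** **Scale.** The safety tabulation has no figure of its own in the plan. The only stated size is the Simon minimax design of Section 9.1 (27 then 8 patients; continue with 19 or more responses, succeed with 25 or more of 35). Exact binomial calculation gives type I error 0.0965 and power 0.9003, so 35 reproduces and is used as N. It sets the scale only; the percentages below do not depend on it.

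**Notation.** N patients start at 800 mg. E of them have a given toxicity at 800 mg, so t = E/N. R of those E are reduced because of it, so s = R/E. The values of t and s are assumptions; the documents give neither for this population.

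**Placement by starting dose.** One column, E/N.

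**Placement by last or lowest dose.** Reduced patients leave the 800 mg column and take the event with them:

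- 800 mg column: (E − R)/(N − R) = t(1 − s)/(1 − ts); N cancels.
- Reduced-dose columns together: R/R = 100% for the triggering event.

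For t = 20%, N = 35, E = 7:

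- s = 25%: 5.25/33.25 = 15.8%
- s = 50%: 3.5/31.5 = 11.1%
- s = 75%: 1.75/29.75 = 5.9%
- s = 100%: 0/28 = 0%

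Over a range of t:

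| True incidence at 800 mg start | s = 25% | s = 50% | s = 75% | s = 100% |
|---|---|---|---|---|
| 13% | 10.1% | 7.0% | 3.6% | 0% |
| 20% | 15.8% | 11.1% | 5.9% | 0% |
| 30% | 24.3% | 17.6% | 9.7% | 0% |
| 40% | 33.3% | 25.0% | 14.3% | 0% |

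The 13% row takes its level from Grade 3 or 4 neutropenia in the Phase 1 study (12 of 90, Section 1.2.2.1) and serves only as a low end. In whole patients: with 10 of 35 affected (28.6%), the 800 mg column reads 5/30 = 16.7% if 5 are reduced and 0/25 if all 10 are.

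**Placement by dose at onset.** The triggering events stay at 800 mg over all starters, so the same example reads 10/35 = 28.6%. Two problems remain. If L further patients first have the event after reduction, the regimen's incidence is (E + L)/N while the 800 mg column still shows E/N. And the 600 mg and 400 mg columns contain only patients already reduced, observed later and for different lengths of time, with the same patient in more than one denominator.

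**Which s is plausible.** Table 2 varies. After a first event it restarts at a lower level for colitis, for Grade 3 or higher liver toxicity, and in the restart rule under the pulmonary heading. After a first Grade 4 neutropenia or thrombocytopenia it resumes at full dose, and it goes down a level only on recurrence. The same recurrence condition applies to withheld diarrhea and to other non-hematologic events of Grade 3 or higher. So s will differ by event and will often be well below 100%.

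**The case against.** The strongest reply is that the direction of any distortion is not fixed. A reader might infer that the tables are bound to make 800 mg look safer, or to show more toxicity at lower doses. The documents do not support that, because they do not state the placement rule. By dose at onset, the reduction-triggering events are counted at 800 mg over all starters, and for those events that is the regimen rate. By starting dose there is no problem at all. A column reading 0% at 800 mg needs both last- or lowest-dose placement and a reduction in every affected patient, which Table 2 does not prescribe. This part of the reply stands.

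The reply can also point to output already planned: the Section 10.3 tables and by-patient listings, the Section 9.6 modification counts and the all-treated safety population. Pooled rates could be recovered from these. But none of them sets the columns, and Section 10.1 is the general rule. A rate that a reader must reconstruct from listings is not a planned summary.

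A reader might also take the treatment-group wording in Section 10.4.1 as a second fault. It is not one: with a single arm it reads naturally as one column of all patients, which is the display wanted.

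Finally, no decision depends on the columns. The suspension rule in Section 6.6 counts patients, the efficacy rule in Section 9.1 counts responses, and no between-dose safety comparison is planned. That is correct and limits the weight of the point.

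**Conclusion.** The point holds as one of analysis and reporting. Section 10.1 prescribes a grouping that is formed after baseline and largely by toxicity, leaves the placement rule undefined, and does not require the incidence for everyone who started at 800 mg.

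The size is conditional. Under last- or lowest-dose placement the 800 mg rate is understated, by an amount that grows with the share of affected patients reduced: a true 20% shows as anything from 15.8% to 0% over shares of 25% to 100%. Under dose at onset, no such understatement arises for the triggering events, but the 800 mg column is incomplete for the regimen and the columns cannot be read as dose effects. Incidences and shares are assumptions. The grouping is largely, not purely, toxicity-driven, because a reduction for an event later judged unrelated can be reversed. Sample size, type I error, power and the stopping rules are untouched.

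**What to change.** Replace the Section 10.1 sentence with wording such as:

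> Safety data will be summarised for the whole safety population as one group (starting dose 800 mg once daily). Adverse events leading to dose delay or reduction will also be tabulated. Dose level at event onset will be given in listings; any summary by dose level at onset, with patient-time at each level, is descriptive only and not for comparison between doses.

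Events causing treatment discontinuation need no new text, since Section 10.3 already tabulates them. Aligning the laboratory wording in Section 10.4.1 with the single group is optional.

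The cost is one sentence, one added table and simpler main tables. It changes no dosing rule and no design parameter. The downside for the sponsor is that the stated rates for 800 mg may look less favourable than under last- or lowest-dose placement.
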